If successful, this project has tremendous opportunity for RO1 level or Program Level National Funding. As we point out in the text, the specific areas we are targeting were the very ones identified by AHRQ in their 2005 report “Knowledge and Access to Information on Recruitment of Underrepresented Populations to Cancer Clinical Trials.” In addition, we have purposely designed this trial to utilize standardized resources (the NCI pamphlet, the PROMIS measures) so that it is readily exportable to other cancer centers across the country. In our opinion, the use of “home grown” messaging and measurements while methodologically appealing, limits the ability to export the intervention to other settings quickly. Finally the PI and Co-PI of this study are well situated to move the findings from this study to a more National level. [name] serves as Chair of the ASCO Health Disparities Advisory group and is a cadre member of the Alliance cooperative group (formerly CALGB, NCTTG, and ACOSOG) health disparities committee. [name] has served in a leadership role on numerous AHRQ-, NIH- and foundation-funded projects and has

received funding from multiple National bodies including ACS, AHRQ, NCI, and NHLBI. This funding includes the use of the Talking Touchscreen technology which indicates that it has already been well received by National Funders.

IV. Preliminary Studies

A. University of Chicago Clinical Trial Study

General Findings: Clinical Trial Participation at the University of Chicago

Funding from an ACS-IRG ([name]) and an ASCO Young Investigator Award ([name]) allowed us to perform a paired survey of physicians and 375 new patients (57% white and 34% African American) seen in the cancer clinics at the University of Chicago Medical Center from September 2008-May 2010 to determine oncologist and patient attitudes toward enrollment in therapeutic cancer clinical trials. ⁴³Of the 375 patients approached, 338 (90%) agreed to participate and returned their survey forms.

In terms of health literacy (using one question health literacy screener¹⁰⁰ with those “quite” and “extremely confident” filling out medical forms classified as having high health literacy) 63% of the sample had high health literacy and 37% low health literacy. Whites were more likely than AA to have high health literacy (79% vs. 57%; $p<0.0001$)

Knowledge of clinical trials in general, differed significantly by both race and health literacy status.

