- High vs. Low HL: 77% vs. 48% ($p<0.0001$)
- White vs. AA: 83% vs. 56% ($p<0.0001$)

Clinical Trial Participation

As shown in **Table 1** below, overall 10% of our patients signed consent for a therapeutic clinical trial with African American patients more likely to sign consent. When a trial is available and offered, 41% of all patients and 63% of our African American patients sign consent. Those with higher health literacy are more likely to sign consent and to sign when offered.

Table 1: Clinical Trial Participation

	All	W	AA	p-value	HHL	LHL	p-value
Signed Consent	10%	10%	18%	0.07	12%	7%	0.2
Clinical Trial Available	57%	61%	46%	0.06	58%	54%	0.69
Offered if Available	35%	36%	31%	0.7	37%	30%	0.47
Signed if Offered	41%	37%	63%	0.2	42%	33%	0.6

W-White; AA-African American; HHH-High Health Literacy; LHL-Low Health Literacy

To better understand the findings regarding African American race and health literacy, we ran a multivariable logistic regression model that controlled for both variables. As displayed in **Table 2**, when controlling for health literacy, AA are 2 times more likely than whites to enroll in a clinical trial. Similarly, those with high health literacy are 2.5 times as likely to enroll as those with low health literacy, controlling for race.

Table 2-Signed Consent: Logistic Regression Models

	OR (bivariate)	95% CI	OR (multivariable)	95% CI
AA:White	1.9	0.9-3.7	2.1	0.8-5.2
HHL:LHL	1.8	0.6-4.9	2.5	0.8-7.8

These data are consistent with our hypothesis that low health literacy is a potential barrier to trial participation. These results also suggest that the impact may be particularly helpful for our African American patients since low health literacy is an intervenable factor which may be dampening what appears to otherwise be enthusiastic support for trial participation in our patient population.

Barriers to Participation

The number one reason that patients did not consent to a trial if offered was that they felt *overwhelmed by the information* (56%). Measured barriers which correlated with not signing consent if offered were lack of social support ($p=0.05$), lack of emotional support ($p=0.01$), high levels of anxiety (OR 0.51; 95% CI 0.13-1.87) and high levels of depression (OR 0.45;95% CI 0.09-2.08). Despite our *a priori* hypothesis that physician trust would play an important role, no measure of physician/institution trust predicted clinical trial enrollment at the University of Chicago.

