2.3 Study Design

V. Study Design and Methodology **Study Type and Sample Size**

This will be a pilot study performed at an urban academic center in south-side Chicago to collect preliminary data in hopes of conducting a larger, randomized intervention. Based on the last two years in our Thoracic oncology clinic at the University of Chicago, we estimate that 600 new patients will be seen over the 2-year period of this study, an amount that will easily provide the number of patients necessary to fulfill the requirement of this pilot study.

For this study, over 2 years, we will contact 150 new lung cancer patients of which 80% (120) will agree to participate in our study. Based on the current clinical trial portfolio in the Thoracic oncology clinic (**see Appendix 5**), which has grown substantially since our last study, it is estimated that trials are now technically available for about 80% of the new patient population (for our pilot of 120 patients that leaves about 100). Of our 100, we estimate, based on our previous work, that a clinical trial will actually be offered to 40% of these patients (40).

Patient Population/Recruitment

All new cancer patients presenting to the University of Chicago outpatient oncology clinics are currently pre-screened for cancer type and set up for appointments by our new patient intake coordinators. New patients with Non-Small Cell Lung cancer and Small Cell carcinoma will be contacted by our study coordinator who will call them 2-3 days prior to their appointment to ascertain their interest in participating in the research study. Those interested will be asked to arrive at their new visit 60-90 minutes prior to the appointment time.

Study Procedure

[figure not shown]
Patients will use the Talking Touchscreen (TT) to complete a pre-intervention survey which will ascertain clinical trial knowledge (detailed in SA#1, surveys in **Appendix 4**) and the following information using the instruments detailed in SA#4: socio-demographics, health literacy, anxiety, depression, and social support. They will then use the TT to view the NCI's educational module on "Taking Part in Cancer Treatment Research Studies". (see **Appendix 3** for a sample screen shot). The NCI

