- Was the patient offered participation in a treatment-related clinical trial?
- If offered, did the patient sign consent?

Actual enrollment in a clinical trial (signed consent) will be confirmed using linkage to our clinical trial database, e-VELOS, which we used successfully in our previous study.

In our previous trial, 40% of patients offered a clinical trial enrolled in a trial. For our low literacy population, 30% enrolled when offered. We expect to be able to improve on these baseline values both by increasing patient understanding of the trial process and by improving their communication with their physician.

Specific Aim 4: To evaluate the associations between socio-demographics, health literacy, patient-reported outcomes (anxiety, depression, social support) and clinical trial enrollment, using the Behavioral Model for Vulnerable Populations.²⁵

Instruments

Tables 3 and 4 contain the instruments we will use:

TABLE 3: PROMIS INSTRUMENTS (www.nihpromis.org)

Construct	Social Support Measure Tools	Scoring for all PROMIS Psychometrics	Background Information/Psychometrics
PROMIS Companionship Scale	PROMIS V 2.0 short form-4 items. .	Reliability: The degree to which a measure is free of error. It can be estimated by the	PROMIS developed several instruments to measure the quality of social support, which refers to functional aspects of supportive relationships, i.e., interpersonal

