	
Psychosocial Measures-Participants will use the TT to complete short forms for anxiety, depression, and social support developed in the Patient-Reported Outcomes Measurement Information System (PROMIS) initiative (www.nihpromis.org). All PROMIS measures are based on T-scores, with a mean of 50 and a standard deviation of 10 in the reference population. Raw scores for this study will be calculated and then transformed to T-scores using PROMIS look-up tables (see http://www.assessmentcenter.net/Manuals.aspx).
 
In addition, the following tumor specific factors will be obtained-cancer type (NSCLC, SCLC), stage, and line of therapy for current stage as ascertained by physician survey but broken down as follows:
 
 • Never treated with chemo • Received first line treatment only • Received second-line treatment • Received three or greater lines of treatment. 
Data Analysis Categorical variables will be summarized as frequency counts and percentages and continuous variables will be summarized as medians and ranges. A logistic regression model will be set up with health literacy (as defined above) as the primary independent variable and enrollment in a clinical trial if one is offered as the primary dependent variable. The second model will control for race, income, cancer stage, line of treatment and co morbidity score.

2.6 Study Duration	Study duration will be 2 years.
2.7 Statistical Analysis and Sample Size Justification	
The principal investigator is supported by a Biostatistics Core Facility offered through the University Chicago's Comprehensive Cancer Center, which provides collaborative statistical support to investigators for the design, conduct, and analysis of clinical trials, observational and population-based studies, and basic science research projects.
 
Variables/Time Points of Interest These are described in detail under each specific aim listed in the Study Procedures section, above.
 
Statistical Methods These are described in detail under each specific aim listed in the Study Procedures section, above.
 
Sample Size: (Power described above under each Specific Aim.) For Specific Aims 1 and 2: Data Analysis

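### Aim 4 promises associations of anxiety, depression and social support with enrollment, but no planned model contains a PROMIS score; secondarily, the adjusted literacy model is thin for about 40 offered patients

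*Combined protocol and SAP*

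**What the plan says.** Specific Aim 4 (sections 2.1 and 2.5) is to evaluate associations between socio-demographics, health literacy, "patient-reported outcomes (anxiety, depression, social support) and clinical trial enrollment". Table 3 lists six PROMIS short forms: four for social support (companionship, emotional, informational, instrumental), one for anxiety and one for depression. Section 2.5 explains how they become T-scores.

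The Data Analysis paragraph under Aim 4 has three elements:
- overall summaries (counts, percentages, medians, ranges);
- a first model: "A logistic regression model will be set up with health literacy (as defined above) as the primary independent variable", with enrollment given an offer as the outcome;
- a second model: "The second model will control for race, income, cancer stage, line of treatment and co morbidity score".

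For variables and methods, section 2.7 only points back: "These are described in detail under each specific aim listed in the Study Procedures section, above". Its sample-size text for Aims 3 and 4 covers one proportion, 0.4 against 0.6, in 40 offered patients.

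**The concern.** An aim is stated, instruments are chosen and scoring is described, but no analysis connects the scores to the outcome. The gap matters because the plan's own earlier survey makes these factors a live question. In section 2.2, under Barriers to Participation: "Measured barriers which correlated with not signing consent if offered were lack of social support" (p=0.05), along with low emotional support (p=0.01), anxiety (OR 0.51, 95% CI 0.13-1.87) and depression (OR 0.45, 95% CI 0.09-2.08). The last two intervals include 1, so the earlier data left those questions open. The pilot is run "to collect preliminary data in hopes of conducting a larger, randomized intervention". As written, it would collect the measures and add nothing on them. If models were chosen after the data were seen, six scores and many possible adjustments would leave room for selective reporting.

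The secondary worry is the size of the adjusted literacy model. Its outcome exists only for patients who are offered a trial, so it rests on about 40 people and not on the 120 enrolled.

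**Working it through.** **1. Promise against analysis.** Factors named in Aim 4: socio-demographics, literacy, anxiety, depression, social support. Terms in model 1: literacy. Terms in model 2: literacy plus the five listed covariates. PROMIS scores in either model: 0 of 6. Items collected: 4 + 5 x 8 = 44. The medians and ranges are not stated to be split by enrollment, and would not estimate an association as described.

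**2. The plan's own power figure.** For one proportion, n=40, 0.4 against 0.6, one-sided 0.05:
- Normal approximation: z = (0.2 x sqrt(40) - 1.645 x sqrt(0.24)) / sqrt(0.24) = (1.265 - 0.806)/0.490 = 0.937, power 0.83.
- Exact rule of at least 22 of 40: alpha 0.039, power 0.791.

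The stated 80% reproduces. It concerns the overall signing rate. No power or precision is given for any Aim 4 regression.

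**3. Size of model 2.**
- Offered patients: 40 in the plan. Low case at the historical 35% offer rate: 120 x 0.80 x 0.35 = 33.6.
- Smaller outcome group at n=40: 40 x 0.40 = 16 (the same at 60% signing); 40 x 0.50 = 20. At n=34 and 40%: 13.6.
- Coefficients: 6 if every covariate is one term; 8 if the four line-of-treatment levels enter as categories; more if race, income or stage have several levels.
- Per coefficient at n=40: 16/8 = 2.0, 20/8 = 2.5, 16/6 = 2.7, 20/6 = 3.3. Low case: 13.6/8 = 1.7.

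**4. What that does to the literacy OR (simulation).**
- From the documents: African American share 34/(34+57) = 37%; high literacy 79% in white and 57% in African American patients; literacy OR from Table 1, signed if offered, (0.42/0.58)/(0.33/0.67) = 1.47; race OR from the same row, (0.63/0.37)/(0.37/0.63) = 2.90. Table 2 gives a literacy OR of 2.5 and a race OR of 2.1, but for a different outcome (signed consent).
- Assumed: binary stage at 60%, normal income and comorbidity, no effect of stage, income, comorbidity or line, and a line split of either 50/25/15/10% or 25% each.

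Median literacy OR at n=40:

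| Fit | True 1 | True 1.47 | True 2.5 |
|---|---|---|---|
| Maximum likelihood, 8 coefficients | 0.96-1.13 | 1.52-1.71 | 3.22-3.61 |
| Maximum likelihood, 6 coefficients | 0.94-1.08 | 1.50-1.66 | 2.87-3.28 |

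Firth with all planned covariates and line collapsed gives 0.93-1.08, 1.38-1.50 and 2.33-2.54.

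- 95% CI factor each way at n=40, true OR 1.47: 6.6-7.2 (8 coefficients), 5.8-6.3 (6 coefficients), 5.4-5.7 (Firth). A further run gave about 7-8 for maximum likelihood and about 6 for Firth. A typical interval is about 0.2-11 with 8 coefficients and about 0.3-8 with Firth.
- Failure of any coefficient at n=40: 32-40% (skewed split), 5-12% (equal split), 1-5% (line as a linear term). Failure of the literacy coefficient itself: about 2-5%, or 4-10% at n=34. Firth with line collapsed: 0.2% or less.
- Dropping race from a reduced Firth model (literacy, stage, treated) moves the median to 1.02-1.27 for a true 1.47 and 1.71-2.05 for a true 2.5, under the assumed race ORs.

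**5. What PROMIS models could deliver.** With SD 10, the approximate factor per 10 points is exp(1.96/sqrt(n p (1-p))). At n=40 and p=0.4 this is exp(1.96/sqrt(9.6)) = 1.88. Simulation of one score plus literacy, with no effect, gives a typical 95% CI of 0.49-2.00 at n=40 and 0.46-2.18 at n=34, with coverage 95-97%. It took scores as independent of race and literacy, and adding race widens the intervals slightly. Putting all six scores into model 2 would give 8 + 6 = 14 coefficients, 16/14 = 1.1 each, which is unworkable.

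**The case against.** This is a self-described pilot and Aim 4 is associational, so low power is acceptable. That stands, and it is why the estimates should be labelled exploratory. It does not supply an analysis that is absent. Appendix 1 is not shown, but section 2.2 describes it as the behavioral model figure with a list of domains, not as an analysis.

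Two stronger readings of the secondary point are tempting. A reader might infer that separation is likely, or that the adjusted literacy OR may well fail to fit. Neither is supported. The 32-40% failure rate needs an assumed skewed split that the documents do not give, and it counts any coefficient, mostly sparse line-of-treatment cells. The literacy coefficient usually stays finite. A reader might also infer that the OR is systematically inflated. At a true OR of 1 it is not.

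It is also fair that Firth narrows the interval only modestly, and that collapsing line of treatment alone would remove most failures. Firth's main gain is less bias when an association exists.

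The case for keeping race should not be overstated. The documents tie it to literacy: "Whites were more likely than AA to have high health literacy" (79% against 57%). They also report "When a trial is available and offered, 41% of all patients and 63% of our African American patients sign consent", but the contrast with white patients (63% against 37%) has p=0.2.

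**Conclusion.** The main point holds on reading alone and depends on no simulation: none of the six PROMIS scores enters either Aim 4 model, so a named part of the aim gets no estimate. The secondary point holds as a matter of precision and bias. With about 2 to 3 outcomes per coefficient, the adjusted literacy OR has 95% limits a factor of about 6 to 8 each way at n=40. By maximum likelihood it drifts away from 1 when an association exists (median 2.9-3.6 for a true 2.5). Some line-of-treatment coefficient may not be estimable, in roughly 5-40% of datasets at n=40 depending on the split. These rates rest on the assumed covariate distributions and are indicative. The point deserves correction before analysis, but does not threaten Aims 1 to 3.

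**What to change.** Amend the Aim 4 analysis, keeping patients offered a trial as the analysis set.

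(a) For each of the six PROMIS T-scores, fit a logistic model of enrollment-if-offered on that score, health literacy and race. Report the OR per 10 points with its 95% CI, labelled exploratory with no multiplicity control. Race is included so that these models and the literacy model treat it alike.

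(b) Keep all planned covariates in the second literacy model, collapse line of treatment to treated or never treated, fit by Firth penalised likelihood, and label it exploratory.

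The cost is six small models on data already collected, and a few sentences of text. The fix does not buy precision: expect about 0.5-2.0 per 10 PROMIS points at n=40 with no effect, slightly wider with race added, and about 0.3-8 for a true literacy OR of 1.47. Collapsing line of treatment gives up control for differences between later lines.

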
2.13 Curriculum Vitae
	
Investigator should provide curriculum vitae in English and a listing of references to Merck/MSD.

**2.13 Protocol
Submission for
Investigator-
Initiated Studies**

U.S. protocols should be submitted by US investigators directly or through the Global Research Specialist at www.merckiiisp.com

Non U.S. protocols should be submitted to the MSD office by the investigators.
